5.1 DATA ANALYSIS AND MANAGEMENT

5.2 Data Analysis: We will be collecting both qualitative and quantitative data during the course of this survey.

5.2.1 Quantitative analyses: Will be conducted using SAS or SPSS statistical software. An odds ratio plus the 95% confidence interval will be calculated to measure the degree of association between retention in care measures and total social capital (all analyses will also be computed for bonding/bridging subscales alone, as well as for item clusters focusing on different dimensions of social capital). Odds ratios will also be calculated to measure the degree of association between other risk factors (education, employment, age, depression, substance use, HIV stigma and CD4 cell count) and patient retention.

Additionally, total social capital will be compared between engaged and non-engaged patients using a two-sided two-sample t-test. Other potential risk factors will be compared between retained and non-retained patients using a chi-square test or Fisher's exact test for categorical covariates and a two-sided two sample t-test for continuous covariates.

Multivariable analyses: Covariates significant to at least $P \leq 0.20$ in the univariable analyses will be used in multivariable logistic regression analyses. Although empirical techniques will be used to identify important covariates, theoretical expectations from our social capital conceptual framework will also augment these decisions. Interactions between covariates will be evaluated, either because suspicions are raised by clinical judgment before the analyses are performed or by statistical examination. Forward stepwise selection will be used if necessary to choose prognostic variables for a multivariable logistic regression model. The odds ratio and its 95% confidence interval will be calculated for each risk factor in the presence of others in the final model.

5.2.2 *Qualitative Data Analysis:* All digitally recorded data will be transcribed verbatim by a professional business transcription service. Qualitative data will be de-identified during this transcription process. Transcripts will then be uploaded into the MaxQDa qualitative data management software (VERBI Software, Berlin, Germany) for further processing and analysis. We will conduct thematic analysis using a combination of inductive and deductive coding. In *deductive coding*, we will apply pre-determined codes from our theoretical model (e.g. collective efficacy) to segments of text that correspond to each theme. In *inductive coding*, we will elicit themes that emerge from the text but were not previously considered (for example, *church community* could come up as a recurring theme among several participants and be added to our code lists). Once the list of themes has been created, we will create a codebook listing the codes and strict definitions to delineate which passages should be labeled with a certain code. The two graduate research assistants (GRAs) will each code 5 transcripts in parallel to determine inter-coder reliability. If any significant disagreements arise in coding, the entire research team will discuss each discrepancy and come to a consensus in order to finalize the codebook. The GRAs will then split and code the remainder of the transcripts. This coding will facilitate further analysis of the transcripts by comparing cases and summarizing comments under each code across participants.

Data collection:

Phase 1- In-depth interviews with YBMSM and key informants: All interviews will take place in a private and quiet room within the IDP clinic or in the case of key informants, at the location of their choosing. [name] has extensive experience conducting such interviews in the clinic for prior research studies and has found this location to be acceptable and comfortable for participants. Interviews will be conducted by a graduate research assistant who will be trained in qualitative methods and interviewing techniques. All interviews will be digitally recorded for subsequent professional transcription. Written informed consent will be obtained before beginning the interview. Interviews will be expected to last approximately 60-90 minutes each. All digitally recorded data will be transcribed verbatim by a professional business transcription service. Qualitative data will be de-identified during this transcription process. Transcripts will then be uploaded into the

MaxQDa qualitative data management software (VERBI Software, Berlin, Germany) for further processing and analysis.

Phase 1- social capital surveys: this data was collected as part of our pilot work prior to the award period. It has already been de-identified and is ready for analysis.

Phase 2 and 3-EMR extraction: Viral load values and appointment attendance data will be extracted from the participants' electronic medical records (EMR) to determine retention and viral suppression outcomes. Clinical data will be entered directly into the Redcap database via a secure online form by graduate research assistants. This will be done at the baseline and 10 month time points.

Phase 2 and 3-surveys: In addition to attending the intervention sessions, participants in both arms will be asked to come to the IDP clinic to participate in three study visits: One at baseline before starting the intervention (0 months), immediately after completing the intervention (around 1 month), 4 months, and a long term follow-up at 10 months after enrollment. The main purpose of these visits will be to complete a survey using the Research Electronic Data Capture (Redcap) online survey platform on an electronic tablet. The Redcap survey will contain our MSCS and will be used to measure change in social capital between the pre- and post-intervention periods. We will also verify the participants' most recent medical care facility (since the last visit) and obtain the participants' signatures on medical record release forms to facilitate abstraction of data on engagement outcomes.

5.3 Data Entry, Editing and Management:

All survey and clinical data will be entered into a password protected, HIPAA compliant RedCap database. The database will be accessible only to the study team. Any subsequent datasets that are exported for analysis will be stripped of identifying information and will only be linked by a participant ID number.

In terms of identifying discrepancies, some of this will be done prospectively by building quality checks into the Redcap data collection system—for example, if certain data do not line up between the baseline and follow up surveys (e.g. participant's date of birth), participants will be prompted to re-enter their answers to that question. Once per month, data will be reviewed in more detail for potential errors. We will ask our biostatistician to conduct descriptive analyses in order to help us identify outliers and return to the original data source as needed to confirm outlying values.

Qualitative interviews will be transcribed verbatim. Identifying information (names) will be taken out at the time of transcription. Files will be kept in a secured shared drive (Emory Box or equivalent) for access by study staff only.

5.4 Provisions for protecting privacy:

Breach of privacy is a concern in this study as identifying information/personal health information will be collected as part of the data collection process. Additionally, efforts to

maximize retention will also include maintaining a database of participants' phone numbers and email addresses. In order to minimize the risk of a privacy breach with any of these files, participants will be assigned a subject ID number which will be used to identify them in the database. Only one file will link the subject ID number to the participants' medical record number, and all files will be password protected, kept on a secure server, and only accessible to the study team. Study files will be kept in password protected files within HIPAA compliant shared drive folders only (e.g. Emory Box). Any paper documents (such as signed informed consent forms) will be kept within a locked file cabinet in the PI's locked office accessible only to key research staff.

5.5. Information management and analysis software:

Data will be collected and stored electronically using the RedCap (Research Electronic Data Capture) program. RedCap is a secure web application for building and managing online surveys and databases. It is compliant with the requirements of HIPAA and therefore ideal for the collection and storage of personal health information such as that which we will be collecting here.

Software for data analysis will include statistical software (SAS, SPSS) as well as qualitative data management software (MaxQDa). We will de-identify all qualitative and quantitative datasets before beginning analyses and will only maintain the de-identified datasets once data collection is completed.

5.6 Quality control/assurance:

All data will be collected by trained staff members. [name] will assume primary responsibility for training and supervision of research staff administering the recruitment, informed consents, and Redcap online questionnaires. Staff will meet for weekly supervision with [name] and her mentors to discuss research protocol and logistical issues, as a way to allow for discussions of adverse events and promote maintenance of study integrity. Data will also be checked periodically for consistency and quality, as described in the *Data entry, editing and management* section above.

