In order to understand which components of social capital are most important for YBMSM and engagement in care, we will draw on quantitative data that is currently being collected with YBMSM in our clinic. [name] successfully competed for a developmental grant from the Emory Center for AIDS Research (CFAR), in which she is beginning to explore social capital among YBMSM at the IDP clinic. The study has a cross-sectional design and participants' involvement involves a single study visit in which they complete an ACASI including our modified social capital scale (MSCS). We also obtained the participants' permission and abstracted data for each patient with respect to appointment adherence, and viral suppression. We can therefore measure associations between engagement outcomes and various dimensions of our social capital measure.

Measure: There is no existing published scale for social capital which has been validated in a United States youth population or in YBMSM more specifically. However, as mentioned above, we have recently modified, pilot tested, and validated Chen's Social Capital Scale to create the MSCS (that we will use in this study). Although Chen's original scale addressed conceptual domains of interest (bonding social capital, bridging social capital, and collective efficacy), it was developed for use among adults in China and therefore contained items that were not culturally relevant to YBMSM. Our MSCS had excellent reliability in an online sample of YBMSM ($\alpha=0.88$; data not yet published). The scale contains subscales for bonding and bridging capital, and it also contains items that specify sources (including family, friends, and LGBT organizations) and types of support (e.g. emotional support, instrumental support and informational support). We can therefore determine which components of individuals' networks are most related to care engagement outcomes using our cross-sectional data.

Sample Size: 80 HIV-positive YBMSM in care at the Grady IDP clinic

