Retention Plan: Our previous experiences have demonstrated the need to pay careful attention to participant retention: part of the role of the study staff is to remind participants about intervention sessions and study visits, scheduling, and discussing any issues they face in the trial procedures. In [name] ongoing work with the Metropolitan Atlanta Community Adolescent Rapid Testing Initiative (MACARTI) trial, these procedures have resulted in at least an 87% retention among participants who were primarily HIV-positive YBMSM (and may be higher as the follow-up period has not yet ended).

Clinical Outcome Measures: Viral load values and appointment attendance will be extracted from the participants' electronic medical records (EMR). The goal is to abstract measures that correspond to the 0 month (baseline) and 10 month (long term follow-up) time points at which participants will be completing surveys. However, we recognize that lab tests (CD4, VL) in the clinical setting may not necessarily be conducted at a time that corresponds to the survey time point. In light of this limitation, and to make the procedures more uniform, we plan the following: (1) the baseline viral load will be the most recent measurement preceding study participation. If this is >6 months prior to the date of enrollment, this will be considered a missing value. (2) The 10 month viral load will be the first value drawn on or after the date that is exactly one year from the beginning of study participation. If this test is done >6 months after the target date, it will be treated as a missing value.

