5.7 Bias in data collection, measurement and analysis

There is potential for bias in data collection, measurement and analysis in this study, which we will make every effort to curtail. Bias in *data collection* is the most likely to be a problem in our study. Selection bias in terms of our initial qualitative interviews (Phase I) and RCT participants could occur, as those YBMSM more interested in our project may already be likely to have higher levels of social capital and be more engaged in care. Given this concern, we propose to expand beyond recruiting at CBOs and in the clinic, and also recruit in more general community settings and online. In terms of *measurement*, our primary outcome will be measured using the MSCS, which has only had limited use in the YBMSM population. Although our preliminary analyses have shown good reliability in other YBMSM samples, it will be important to continue to examine the performance of this measure in this population. Finally, in terms of *analysis*, the qualitative analysis is prone to bias given the inherent subjectivity in qualitative research. In order to counteract this, we will utilize a team approach to qualitative coding and interpretation, and we will

undertake member checking with our YCAB to ensure that our interpretation of our qualitative data is consistent with their general experiences.

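### In the trial data, the planned social capital–retention odds ratio may be confounded by prior engagement, which is measured at baseline but not among the named covariates

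*Combined protocol and SAP*

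**What the plan says.** Section 5.2.1 (Quantitative analyses) estimates "the degree of association between retention in care measures and total social capital". It then examines "other risk factors (education, employment, age, depression, substance use, HIV stigma and CD4 cell count) and patient retention". Covariates reaching P≤0.20 univariably go forward to a multivariable logistic model, with forward stepwise selection if needed. The choice is not purely empirical, since "theoretical expectations from our social capital conceptual framework will also augment these decisions".

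The trial collects three measures of engagement at entry:

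- **Viral load.** Section 2.3 (Clinical Outcome Measures) says "the baseline viral load will be the most recent measurement preceding study participation". If that value is more than 6 months "prior to the date of enrollment, this will be considered a missing value".
- **Retention and adherence.** Table 2 lists both at 0 and 10 months.
- **Record extraction.** Section 5.2 says of the EMR data on viral load and attendance: "This will be done at the baseline and 10 month time points".

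Section 4.4 states the question behind these models: whether raising social capital has an effect on care engagement.

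**The concern.** Social capital is not randomised; only the arm is. A man already settled in care may report more support and may also be more likely to stay in care over the next 10 months. If so, a model without prior engagement credits social capital with some of what prior engagement explains. That matters for the Section 4.4 question, because prior engagement is the most obvious competing explanation for an association. The trial holds the data to address it, but the plan leaves its use to discretion.

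**Working it through.** **The plan's own figure.** No power or precision is stated for this odds ratio. The only sample size is for the primary outcome in Section 3.5: 53 per arm for a 15% increase from 26.6 with SD 7.0, so d = 0.15 × 26.6 / 7.0 = 0.57. A two-sided 5% t-test at 80% power needs 50 per arm. Allowing for Mann–Whitney efficiency gives 50 × π/3 = 52.4, hence 53, although the documents name no test. The figure is sound but does not bear on this point.

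**Inputs from the documents.** N = 120. Follow-up is 87% in the team's earlier trial (Section 2.3), so 120 × 0.87 = 104 men. Viral suppression of 46% and 72% (Section 1.2.4) serves here as a range for the share engaged at baseline.

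**Assumed, not in the documents.** 60% retained; correlation ρ of social capital with baseline engagement 0 to 0.5; odds ratio of baseline engagement for retention 3 to 8; true social capital odds ratio 1.0.

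**Hand approximation.** With p the share engaged, the slope of baseline engagement on one SD of social capital is ρ√(p(1−p)). The apparent odds ratio under the null is then about exp(ρ × √(p(1−p)) × ln OR). For p = 0.72, √(0.72 × 0.28) = 0.449. With ρ = 0.3 and OR = 3: exp(0.3 × 0.449 × 1.099) = exp(0.148) = 1.16.

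**Large-sample logistic regression** (400,000 simulated records, standard errors scaled to n = 104, 72% engaged, true odds ratio 1.0):

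| ρ | Baseline OR | Unadjusted OR (SE of log OR) | Adjusted OR (SE) | SE ratio |
|---|---|---|---|---|
| 0 | 3 | 1.00 (0.200) | 1.00 (0.207) | 1.03 |
| 0 | 8 | 1.00 (0.200) | 1.00 (0.223) | 1.11 |
| 0.1 | 3 | 1.05 (0.200) | 1.00 (0.207) | 1.04 |
| 0.1 | 8 | 1.09 (0.201) | 1.00 (0.224) | 1.11 |
| 0.3 | 3 | 1.16 (0.202) | 1.00 (0.216) | 1.07 |
| 0.3 | 8 | 1.31 (0.205) | 1.00 (0.234) | 1.14 |
| 0.5 | 3 | 1.28 (0.204) | 1.00 (0.238) | 1.17 |
| 0.5 | 8 | 1.60 (0.214) | 1.00 (0.256) | 1.20 |

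With 46% engaged the results are close: 1.18 and 1.32 at ρ = 0.3, and 1.31 and 1.61 at ρ = 0.5. Across all settings the adjusted standard error is 1.00 to 1.20 times the unadjusted one. It never falls.

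**Imperfect adjustment.** The adjusted value of 1.0 arises because the simulation adjusts for the only confounder, measured without error. In a separate setting (60% engaged, a 0.8 SD gap in social capital, retention 85% v 50%) the unadjusted odds ratio is 1.36. A marker that classifies engagement correctly 80% of the time brings it only to 1.25, and one correct 90% of the time to about 1.14. The covariate should therefore be the closest available to the outcome.

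**Room in the model.** With 60% of 104 retained, 104 × 0.4 ≈ 42 men are not retained. Social capital plus seven covariates, at one parameter each, gives 42/8 ≈ 5 per parameter. One further term gives 42/9 ≈ 4.7, and three give 42/11 ≈ 3.8.

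**The case against.** Several points on the other side stand.

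- **The list is not closed.** Theory may add covariates, and CD4 count, a partial proxy for engagement, is already named. This leaves the adjustment possible but not planned.
- **The text comes from elsewhere.** Section 5.2.1 repeats the Part 1c plan for 80 men, of which Section 2.1 says "The study has a cross-sectional design". Those data have no separate baseline, so the omission is no fault there. But 5.2.1 is the only quantitative analysis section, so it is also all that the trial data have.
- **Section 5.7 can be over-read.** It says certain men "may already be likely to have higher levels of social capital and be more engaged in care", but the men meant are those keener to join. That describes selection into the study. A reader might infer that the protocol concedes a correlation among enrolled men, but it does not.
- **Upward bias is not established.** A reader might infer that the odds ratio is certainly inflated. Size and direction depend on correlations that the documents do not report.
- **Precision is not being thrown away.** A reader might infer that it is. For this odds ratio the standard error stays the same or grows with adjustment. A gain could be argued for an arm comparison of viral suppression, but 5.2.1 contains none. A randomised arm comparison would not be confounded by baseline engagement either.
- **Adjustment can remove real effect.** The protocol sees social capital as acting through support, so engagement at entry may partly result from earlier social capital.

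**Conclusion.** The point holds in limited form. Prior engagement is measured at entry, is absent from the named covariates, and is a plausible confounder of a non-randomised association in the trial data. Under assumed correlations of 0.1 to 0.5 and baseline odds ratios of 3 to 8, a null could appear as about 1.05 to 1.6 per SD; at zero correlation nothing is lost. All of that range rests on assumed inputs. The case for acting is that the adjustment is pre-specifiable, uses values already collected, and bears directly on the Section 4.4 question. It does not extend to the pilot analysis.

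**What to change.** In Section 5.2.1, for the RCT data only:

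1. Force the baseline value of the outcome into each engagement model, exempt from the P≤0.20 screen: baseline retention for retention, the month-0 self-report item for adherence, and baseline viral status for suppression.
2. Code baseline viral status as suppressed, not suppressed, or no test in the prior 6 months. The 6-month rule otherwise makes the value missing, and a complete-case model would drop men who may be the least engaged.
3. Define the look-back period for baseline retention. Section 4.2 defines retention only within the 10-month study period.
4. Let the forced terms replace the forward stepwise search, since events per parameter are few.
5. State the visit at which social capital enters the model.
6. Report the unadjusted odds ratio alongside, because adjustment may remove social capital effects that acted before baseline.

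The cost is a few sentences, one or two degrees of freedom per model and a somewhat wider interval (standard error up to 20% larger in the settings above). No new measurement is needed.

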1.5.1 Aims and Hypothesis

Aim 1: To characterize the social networks of YBMSM living with HIV with respect to the multiple dimensions of social capital using a mixed-methods research design.

Aim 2: To develop a social capital-based intervention to enhance engagement in care among HIV-positive YBMSM utilizing a participatory, youth-centered approach.

[figure not shown]
Aim 3: Implement a randomized controlled trial with groups of HIV-positive YBMSM to develop and pilot our social capital interventions.

Aim 3a: To assess participant satisfaction and feasibility of the intervention.

Aim 3b: To test impact on social capital and HIV care engagement outcomes.

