Data Analysis: An odds ratio plus the 95% confidence interval will be calculated to measure the degree of association between retention in care measures and total social capital (all analyses will also be computed for bonding/bridging subscales alone, as well as for item clusters focusing on different dimensions of social capital). Odds ratios will also be calculated to measure the degree of association between other risk factors (education, employment, age, depression, substance use, HIV stigma and CD4 cell count) and patient retention. Additionally, total social capital will be compared between engaged and non-engaged patients using a two-sided two-sample t-test. Other potential risk factors will be compared between retained and non-retained patients using a chi-square test or Fisher's exact test for categorical covariates and a two-sided two sample t-test for continuous covariates.

Multivariable analyses: Covariates significant to at least $P \leq 0.20$ in the univariable analyses will be used in multivariable logistic regression analyses. Although empirical techniques will be used to identify important covariates, theoretical expectations from our social capital conceptual framework will also augment these decisions. Interactions between covariates will be evaluated, either because suspicions are raised by clinical judgment before the analyses are performed or by statistical examination. Forward stepwise selection will be used if necessary to choose prognostic variables for a multivariable logistic regression model. The odds ratio and its 95% confidence interval will be calculated for each risk factor in the presence of others in the final model.

Timeline and feasibility: Given that this data will already be collected, when the MARI award period begins, and utilizing the statistical support that we have included in our budget, we expect to be able to complete this statistical analysis within the first 6 months of the project period.

Part 1d: Key Informant Interviews

To answer this question, we will conduct IDIs with up to 30 key informants who have experience and interest in working with YBMSM living with HIV. Key informants may include healthcare workers (HCWs) and representatives of community-based organizations (CBOs) who work with YBMSM.

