3.2.3 Exclusion Criteria

- Age $<$ 18 years or \geq 30 years
- Unwilling or unable to provide written informed consent
- Enrollment in one phase of the study is an exclusion criteria for enrollment in other phases

3.3 Justification for inclusion/exclusion criteria: We are focusing exclusively on YBMSM in this study due to the disproportionate impact of HIV in this population, as detailed in the literature review above. We are aiming to develop an intervention that is culturally and developmentally appropriate, and as such are limiting our enrollment to this target population.

3.4 Estimated number of participants: We plan to enroll 180 total participants (120 in the randomized controlled trial and 60 in preliminary interviews).

3.5 Sampling, including sample size and statistical power:

Based on our MSCS scale characteristics in our previous online survey study (mean 26.6, standard deviation 7.0), we can estimate that a sample size of n=106 (n=53 in each of the intervention and control groups) would allow us to detect approximately a 15% increase in social capital attributable to our intervention (using 80% statistical power). For the RCT, we will therefore aim to recruit n=120 patients (accounting for some attrition): based on our team's previous work in the same geographic area, we believe this to be a feasible number of YBMSM to recruit during the specified time period from our IDP clinic and community partners.

Table 1. Power calculation

Control Patients	Intervention Patients	Control SC Mean	Intervention SC Mean	Detectable Effect Size	Detectable Percent Increase in SC
31	31	26.6	31.9	0.75	20%
39	39	26.6	31.3	0.67	17.5%
50	50	26.6	30.7	0.58	15.4%
53	53	26.6	30.6	0.57	15%
77	77	26.6	29.9	0.47	12.5%
114	114	26.6	29.3	0.38	10%

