Psychological Distress	Brief Symptom Inventory	53	Phase III: RCT participants at 0, 4 and 10 months

Outcome Measures: The primary outcome measure will be social capital. The core measure of social capital that we will use is our Modified Social Capital Scale (MSCS) described above, which we developed and validated exclusively with YBMSM. Our aim is to discover whether social capital improves as a result of being in the social capital intervention, and also to see if there is any similar effect in the control arm. Secondary outcomes will be measures of HIV care engagement, namely: (1) Retention in care, (2) Adherence to medications, and (3) HIV viral load suppression. As per Institute of Medicine (IOM) recommendations, **retention in care** will be measured by determining, within the 10 months of the study period, (a) participation in continuous care, that is, at least two or more routine HIV visits at least three months apart, (b) receiving two or more CD4 tests, and (c) receiving two or more viral load tests.⁶⁰ **Adherence to antiretroviral medications** will be measured using a composite of single item self-report question and pharmacy refill records. **HIV viral suppression** will be considered achieved if the medical records report a viral load below the level of detection for the site-specific assay. Viral load values and appointment attendance will be extracted from the participants' EMR.

4.3 Intervention Content: As the details of the intervention will be influenced greatly by the formative research and the input of the YCAB, it cannot be described in full detail at this time. The main intervention delivery will consist of either a one day or a consecutive two day group

meeting among the YBMSM with time divided between health education and community photovoice project planning. Each group will contain ten YBMSM; we plan for six groups each in the control and intervention arms. As detailed above, the intervention will consist of a group-based curriculum in program planning and HIV education, culminating in the planning and implementation of a community photovoice project.

4.4 Outcomes: The primary outcome of interest for the RCT will be social capital, as we are aiming to determine whether or not our intervention is effective in increasing social capital. We will also look at engagement outcomes, to determine whether or not increasing social capital has an impact on care engagement in our participants.

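### Section 5.2.1 repeats the cross-sectional Part 1c analysis, so no stated analysis estimates the intervention effect on the primary outcome

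*Combined protocol and SAP*

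**What the plan says.** **The stated analysis.** Section 5.2.1 names the software and then gives:
- odds ratios relating retention to social capital and to other risk factors;
- a t-test in which "total social capital will be compared between engaged and non-engaged patients using a two-sided two-sample t-test";
- comparisons of risk factors between retained and non-retained patients;
- a covariate screen at P ≤ 0.20, followed by multivariable logistic regression with forward stepwise selection if needed.

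Section 2.1, Part 1c (Data Analysis) gives the same list for the earlier survey of 80 patients, beginning with odds ratios to "measure the degree of association between retention in care measures and total social capital".

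**The question the trial asks.** Aim 3b is "To test impact on social capital and HIV care engagement outcomes". Section 3.5 says that 106 participants "would allow us to detect approximately a 15% increase in social capital attributable to our intervention", at 80% power. Section 4.4 makes social capital the primary outcome and says "we are aiming to determine whether or not our intervention is effective in increasing social capital". Section 4.2 (Outcome Measures) asks whether social capital improves because of the intervention, "and also to see if there is any similar effect in the control arm".

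**The visits.** Section 2.3 and Table 2 place the MSCS at 0, 1, 4 and 10 months. None is called primary.

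**The concern.** An analyst who follows section 5.2.1 compares people who stay in care with people who do not. That is a non-randomized association. It bears on the secondary question in section 4.4 (whether more social capital goes with better engagement), but it does not use the randomization and says nothing about whether the intervention raised the MSCS.

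The analysis that does answer the primary question has to be pieced together from other sections. They leave open the visit, the form of the outcome, the population, the alpha and the treatment of missing MSCS values. Several defensible analyses therefore remain available, and nothing in the plan prevents the choice from being made after the results are known.

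**Working it through.** **1. Section 5.2.1 against Part 1c.** Apart from the software sentence in 5.2.1, the two texts match nearly word for word: the same odds ratios, t-test, chi-square or Fisher tests, P ≤ 0.20 screen and stepwise logistic model. Part 1c concerns a single-visit survey with no randomization, so its text has no place for arm or visit. Section 5.2.1 adds none.

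**2. What other sections imply about the between-arm contrast.**
- Table 1 (section 3.5) sets a control mean beside an intervention mean. Its effect sizes match the mean difference over the raw SD: (30.6 − 26.6)/7.0 = 0.57. That implies unadjusted follow-up means.
- The survey paragraph under section 5.2 describes measuring pre-to-post change, and section 5.8 speaks of differences between arms in improvement. That implies change from baseline, by an unstated estimator.
- No section names the test, primary visit, analysis population or alpha. Section 2.3 has a missing-value rule for viral load, but there is none for the MSCS.

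**3. Does the sample size reveal the intended test?** Inputs from section 3.5: SD 7.0, difference 0.15 × 26.6 = 3.99, power 80%, 53 per arm. Alpha has to be assumed; take two-sided 0.05.
- Normal approximation: n = 2(1.960 + 0.842)² × 7.0²/3.99² = 48.3, so 49 per arm.
- Exact two-sample t-test: 50 per arm. Power at 53 is 82.8%.
- One-sided 0.05 gives 39 and two-sided 0.01 gives 72 (normal approximation).
- Rank-test formulas give 52 (t-test n × π/3) or 54 (Noether).

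The figure 53 is slightly conservative for a t-test and close to a rank test that the plan never names. It does not identify the analysis.

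**4. What an unnamed visit is worth.** Simulated null trials: 53 per arm, no clustering, baseline plus three visits with equal correlation r (assumed), 20,000 trials per setting, two-sided 0.05. The table shows the proportion with at least one of three visits significant.

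| Outcome form | r = 0.3 | r = 0.5 | r = 0.7 |
|---|---|---|---|
| Follow-up value | 13.3% | 12.5% | 10.9% |
| Change score | 12.4% | 12.9% | 12.5% |
| Baseline-adjusted | 13.5% | 13.3% | 13.4% |
| One fixed visit, baseline-adjusted | 4.6% | 5.1% | 5.4% |

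A second simulation gave 10.5% to 13.9% for the best of three visits. The range is about 11% to 14%, against about 5%.

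**5. What the repair does to the power statement.** Detectable difference at 80% power from the noncentral t, two-sided 0.05:
- No clustering: SE = 7.0 × √(2/53) = 1.360; detectable 3.85 points; 3.85/26.6 = 14.5%. The plan states 15%.
- Six groups per arm, assumed intraclass correlation (ICC) 0.05: design effect = 1 + (53/6 − 1) × 0.05 = 1.392; SE = 7.0 × √(2 × 1.392/53) = 1.604; 10 degrees of freedom; detectable 4.99 points = 18.8%.
- The same with an assumed baseline correlation of 0.5 (variance × (1 − 0.5²)): SE = 1.389; detectable 4.32 points = 16.2%. If baseline explains only within-group variation, the figure is 17.1%.

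**The case against.** The best defence is that the intent is plain. Table 1 is a two-arm comparison of MSCS means, section 5.8 speaks of a between-arm difference in improvement, and Aim 3 is described partly as a pilot. This stands as far as it goes. A reader might infer that no between-arm comparison was planned, and the documents do not support that. But intent does not fix an analysis, and the two hints differ. The pilot label is limited by Aim 3b and by a power calculation for efficacy.

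Three other strong readings also go too far:
- **That the analysis has been, or will be, chosen on the results.** Part 1b mentions people who have already been through the arms, section 5.8 allows additional analyses for meetings, and section 6.0 foresees interim results. This is suggestive only. The reviews that 5.8 lists concern comparability, accrual, retention and data quality, and section 6.0 covers every phase, including the qualitative work. Nothing says that outcomes were examined by arm. For the same reason, larger error rates built on a search across outcome forms as well as visits would be strained.
- **That the sample size is wrong.** Under a t-test it is slightly conservative if participants are independent.
- **That the control-arm remark in section 4.2 sets up a rival within-arm primary analysis.** It may only describe the comparator side of a two-arm comparison. It needs a stated rank, no more.

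**Conclusion.** The concern holds. The only stated quantitative analysis that could serve the trial does not estimate the intervention effect on the MSCS, and the implied between-arm comparison is neither consistent across sections nor specified. This goes beyond missing detail, because the analysis written down answers a different question. It should be corrected before outcomes are examined by arm.

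The finding rests on the text, not on the simulation. The 11% to 14% shows what one open choice, the visit, could be worth if the best were reported; it is not a prediction of what the team will do. It depends on an assumed alpha, assumed between-visit correlations and no clustering.

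**What to change.** Limit the present 5.2.1 text to Part 1c and to an exploratory analysis of the section 4.4 question on social capital and engagement. Then add a trial analysis, stated before outcomes are examined by arm, including for any interim presentation:

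- **Primary comparison:** MSCS total between arms by intention to treat, at one visit named by the sponsor and at a stated two-sided alpha. If the 10-month visit is chosen, settle its starting point, which sections 2.3 and 5.2 give variously as start of intervention, study completion and enrollment.
- **Model:** adjust for baseline MSCS, which is already collected, and account for delivery groups and repeated visits. One example is a linear mixed model with arm, visit, arm-by-visit and baseline MSCS, random effects for group and participant, and small-sample degrees of freedom based on the groups actually formed. A change score would also be valid, but its variance factor 2(1 − r) is never below the 1 − r² of baseline adjustment.
- **Missing follow-up:** state the assumption and a sensitivity analysis.
- **Secondary:** other visits, subscales and within-arm change, including the control-arm look. Compare engagement outcomes by arm.
- **If outcomes by arm have already been examined:** say so and label the analysis accordingly.

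The cost is one rewritten section and modest programming, with no new data or participants. The price is a less favourable power statement once groups are modelled. At an assumed ICC of 0.05 with six groups per arm, the detectable increase is about 18.8%, or 16.2% with an assumed baseline correlation of 0.5, against the stated 15%. The documents give neither an ICC nor a correlation, so the sponsor should supply its own values. Naming one visit also gives up the freedom to lead with another.
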